#### 8.3.4 TIME PERIOD AND FREQUENCY FOR EVENT ASSESSMENT AND FOLLOW-UP

The occurrence of an adverse event (AE) or serious adverse event (SAE) may come to the attention of study personnel during study visits and interviews of a study participant presenting for medical care, or upon review by a study monitor.

All AEs including local and systemic reactions not meeting the criteria for SAEs will be captured on the appropriate case report form (CRF). Information to be collected includes event description, time of onset, clinician's assessment of severity, relationship to study product (assessed only by those with the training and authority to make a diagnosis), and time of resolution/stabilization of the event. All AEs occurring while on study must be documented appropriately regardless of relationship. All AEs will be followed to adequate resolution.

Any medical condition that is present at the time that the participant is screened will be considered as baseline and not reported as an AE. However, if the study participant's condition deteriorates at any time during the study, it will be recorded as an AE.

Changes in the severity of an AE will be documented to allow an assessment of the duration of the event at each level of severity to be performed. AEs characterized as intermittent require documentation of onset and duration of each episode.

The study coordinator will record all reportable events with start dates occurring any time after informed consent is obtained until 7 (for non-serious AEs) or 30 days (for SAEs) after the last day of study participation. At each study visit, the investigator will inquire about the occurrence of AE/SAEs since the last visit. Events will be followed for outcome information until resolution or stabilization.

#### 8.3.5 ADVERSE EVENT REPORTING

The group of investigators, including the principal investigator, and the research support staff will carry out monitoring of all AEs. These will be captured on the appropriate case report form (CRF). Data will be reviewed quarterly to ensure that it is accurate, complete, and that its collection is in compliance with the protocol. There will also be a continual assessment of the risks and benefits.

#### 8.3.6 SERIOUS ADVERSE EVENT REPORTING

The study investigator shall complete an Unanticipated Adverse Device Effect Form and submit to the study sponsor and to the reviewing Institutional Review Board (IRB) as soon as possible, but in no event later than 10 working days after the investigator first learns of the effect. The study sponsor is responsible for conducting an evaluation of an unanticipated adverse device effect and shall report the results of such evaluation to the Food and Drug Administration (FDA) and to all reviewing IRBs and participating investigators within 10 working days after the sponsor first receives notice of the effect. Thereafter, the sponsor shall submit such additional reports concerning the effect as FDA requests.

#### 8.3.7 REPORTING EVENTS TO PARTICIPANTS

N/A

### 8.3.8 EVENTS OF SPECIAL INTEREST

N/A

### 8.3.9 REPORTING OF PREGNANCY

N/A

## 8.4 UNANTICIPATED PROBLEMS

### 8.4.1 DEFINITION OF UNANTICIPATED PROBLEMS (UP)

The Office for Human Research Protections (OHRP) considers unanticipated problems involving risks to participants or others to include, in general, any incident, experience, or outcome that meets all of the following criteria:

- Unexpected in terms of nature, severity, or frequency given (a) the research procedures that are described in the protocol-related documents, such as the Institutional Review Board (IRB)-approved research protocol and informed consent document; and (b) the characteristics of the participant population being studied;
- Related or possibly related to participation in the research (“possibly related” means there is a reasonable possibility that the incident, experience, or outcome may have been caused by the procedures involved in the research); and
- Suggests that the research places participants or others at a greater risk of harm (including physical, psychological, economic, or social harm) than was previously known or recognized.

This definition could include an unanticipated adverse device effect, any serious adverse effect on health or safety or any life-threatening problem or death caused by, or associated with, a device, if that effect, problem, or death was not previously identified in nature, severity, or degree of incidence in the investigational plan or application (including a supplementary plan or application), or any other unanticipated serious problem associated with a device that relates to the rights, safety, or welfare of subjects (21 CFR 812.3(s)).

### 8.4.2 UNANTICIPATED PROBLEM REPORTING

The investigator will report unanticipated problems (UPs) to the reviewing Institutional Review Board (IRB). The UP report will include the following information:

- Protocol identifying information: protocol title and number, PI's name, and the IRB project number;
- A detailed description of the event, incident, experience, or outcome;
- An explanation of the basis for determining that the event, incident, experience, or outcome represents an UP;
- A description of any changes to the protocol or other corrective actions that have been taken or are proposed in response to the UP.

To satisfy the requirement for prompt reporting, UPs will be reported using the following timeline:

- UPs that are serious adverse events (SAEs) will be reported to the IRB as soon as possible, but in no event later than 10 working days after the investigator first learns of the event.
- Any other UP will be reported to the IRB and to the study sponsor within 3 days of the investigator becoming aware of the problem.

- All UPs should be reported to appropriate institutional officials (as required by an institution's written reporting procedures), the supporting agency head (or designee), and the Office for Human Research Protections (OHRP) within 24 hours of the IRB's receipt of the report of the problem from the investigator.

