### 2.2 BACKGROUND

The most commonly reported symptoms include urgency, urinary frequency, dysuria, incontinence, hematuria, suprapubic discomfort, fever due to urinary tract infections and flank pain and they can occur in up to 80% of stented patients. Sometimes, the symptoms are poorly tolerated and can negatively affect the patient's quality of life [2, 3].

Shao et al have studied the relationship between bladder filling and the renal pelvic pressure (RPP) in stented patients, which revealed that RPP increases mildly during bladder filling and dramatically during voiding, indicating the occurrence of urinary reflux. As a result, the authors encouraged early removal of the stents [4]. Another study showed that patients with stents whose distal coils cross the midline are at higher risk of post-stenting morbidities [5].

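### Section 8.4.2 allows longer to report a serious unanticipated problem than a non-serious one and omits the sponsor from the serious route, and SAEs that are not unanticipated have no reporting deadline

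*Combined protocol and SAP*

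**What the plan says.** Section 8.4.2 has three timing rules.

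- For serious UPs: "UPs that are serious adverse events (SAEs) will be reported to the IRB as soon as possible", and "in no event later than 10 working days after the investigator first learns of the event". The sponsor is not mentioned.
- For the rest: "Any other UP will be reported to the IRB and to the study sponsor within 3 days" of the investigator becoming aware.
- For all UPs, an onward report to institutional officials, the supporting agency head and OHRP, due "within 24 hours of the IRB's receipt of the report of the problem from the investigator".

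Section 8.3.6 carries the heading Serious Adverse Event Reporting, but its text concerns only UADEs: "The study investigator shall complete an Unanticipated Adverse Device Effect Form and submit to the study sponsor" and to the IRB, as soon as possible and within 10 working days. Section 8.4.1 says that a UADE may count as a UP.

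For adverse events in general, 8.3.5 provides CRF capture, monitoring by the investigators and research staff, and a periodic check: "Data will be reviewed quarterly to ensure that it is accurate, complete, and that its collection is in compliance with the protocol". It adds an ongoing weighing of risks and benefits, with no timing. Section 8.3.4 has SAEs recorded if they begin up to 30 days after participation ends. Section 8.3.3.3 makes the PI and the sponsor responsible for deciding whether an event was expected.

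**The concern.** A prompt-reporting rule would normally give the most serious events the shortest limit and at least as many recipients. Here the order is reversed, and the protocol gives no reason. An investigator who follows 8.4.2 to the letter may take about two weeks over a serious UP but must report a minor one within days.

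The second issue is coverage. Both timed routes (8.3.6 and 8.4.2) require the event to be classed as unanticipated. Once an SAE is judged expected, no stated rule brings it to the sponsor or the IRB by any date. The sponsor shares the judgment of expectedness under 8.3.3.3, and under 8.3.2 its view can make an event serious. Without timely notice it cannot exercise either role.

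The stake is timely safety oversight. The trial is open label (4.1), no interim analysis is planned (9.4.6), and safety oversight rests with the investigators and their staff (10.1.5). Section 10.1.1 lists unacceptable risk as a ground for suspension, which presupposes that serious events are seen promptly. The efficacy analysis is not affected.

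**Working it through.** The plan states no figure to reproduce. The check sets the rules side by side and converts working days to calendar days, ignoring public holidays.

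**Rules by type of event**

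| Event | Rule | Recipients of the investigator's report | Outer limit |
|---|---|---|---|
| UP that is an SAE | 8.4.2, first timing bullet | IRB | 10 working days |
| Any other UP | 8.4.2, second timing bullet | IRB and sponsor | 3 days |
| UADE | 8.3.6 | Sponsor and IRB | 10 working days |
| SAE that is neither a UP nor a UADE | 8.3.4, 8.3.5 | none named | none |

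**Length of the limits**

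1. Ten working days from a weekday is two full weeks: 2 × 7 = 14 calendar days. From a Saturday it is 13 and from a Sunday 12.
2. The protocol does not say whether the 3 days are calendar or working days. As calendar days they are 3. As working days they are 3 to 5 calendar days, depending on the weekday.
3. Difference from a weekday start: 14 − 3 = 11 at most and 14 − 5 = 9 at least.
4. From a weekend start, with calendar days: 13 − 3 = 10 (Saturday) and 12 − 3 = 9 (Sunday). With working days: 13 − 4 = 9 and 12 − 3 = 9.

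The serious-UP ceiling is 9 to 11 calendar days longer under every reading.

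**Does the onward step repair the order?** No. Its 24 hours run from the IRB's receipt, so it adds up to one day to whichever limit applied first: 14 + 1 = 15 days for a serious UP from a weekday start, against 3 + 1 = 4 for any other UP with calendar days.

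**Does 8.3.6 close the sponsor gap?** Only in part. It sends UADEs to the sponsor, so a serious UP that is also a UADE reaches both parties. The ceiling is still 10 working days, so the order of the limits stays reversed for the sponsor too. A serious UP that is not a UADE, for example one caused by a study procedure, has no stated route to the sponsor.

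**Does anything time an expected SAE?** The 30 days in 8.3.4 define which events are recorded, not when they are reported. The quarterly review in 8.3.5 is described as a check on data quality and compliance. The ongoing risk-benefit assessment has no interval. None of these sets a date for the sponsor or the IRB.

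**The case against.** The strongest reply is that the protocol is less bare than its bullets suggest. In a stent trial many serious UPs would be device-related and fall under 8.3.6, which names the sponsor. All UPs also go onward to institutional officials, the agency head and OHRP. The serious-UP rule asks for reporting as soon as possible, so 10 working days is a ceiling and not the expected delay. The investigators monitor all adverse events, ask about them at each visit and weigh risk and benefit continually.

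Much of this stands, and it rules out three stronger readings that a reader might infer.

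- *That serious UPs reach the IRB alone.* Section 8.3.6 and the onward bullet contradict this. The sponsor gap is confined to serious UPs that are not UADEs.
- *That an admission for a complication named in Section 2.2 certainly has no clock.* That section says of a list of symptoms ending in "fever due to urinary tract infections and flank pain and they can occur in up to 80% of stented patients". It describes symptoms, not admissions. Sections 8.3.3.3 and 8.4.1 let an event be unexpected by severity or frequency, so such an admission could still qualify as a UP. Whether it does is a matter of judgment.
- *That the delay converts into a number of further patients exposed, or can be measured against the follow-up schedule.* The protocol gives no accrual period: the synopsis states one year for both study and participant duration. Investigators may act between quarterly reviews, and the reporting clock starts when the investigator learns of the event, not at stent placement.

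The reply does not change the reversed ceilings, the missing sponsor in the serious bullet, or the missing deadline for SAEs outside both categories.

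**Conclusion.** The point holds in three parts.

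1. The outer limit for a serious UP is 9 to 11 calendar days longer than for any other UP.
2. Section 8.4.2 names the sponsor for non-serious UPs but not for serious ones, and 8.3.6 fills that gap for UADEs only.
3. An SAE judged to be neither a UP nor a UADE has no deadline for reaching the sponsor or the IRB.

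The first part is a stated rule that allows slower safety reporting if followed, and not merely missing detail. The day counts assume no public holidays and cover both readings of the 3 days. The finding concerns ceilings; actual reporting may be faster. It also takes the sponsor to be a party distinct from the investigator, as 8.3.6 and 8.4.2 do in naming it as a separate recipient. The change should be made, but it bears on oversight and not on the validity of the efficacy comparison.

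**What to change.** Reconcile 8.3.5, 8.3.6 and 8.4.2.

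- In 8.4.2, make the deadline for UPs that are SAEs no longer than the 3 days already set for other UPs, with the same recipients (IRB and sponsor). State whether these are calendar or working days.
- Keep 10 working days only as the outer limit for the formal UADE report in 8.3.6. Say there that a UADE which is also a serious UP still needs the earlier notice under 8.4.2.
- In 8.3.6, state a route and a deadline to the sponsor for SAEs that are not UADEs, whether or not they were expected. The documents do not fix this period, so the sponsor and the IRB should choose it.
- In 8.3.5, refer to those routes so that the quarterly review is not read as the only path for an SAE.

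The cost is a few sentences and faster paperwork for what should be a few events in a 50-patient, single-site trial. No design, sample size or analysis element changes.

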#### 8.4.3 REPORTING UNANTICIPATED PROBLEMS TO PARTICIPANTS

*Cystogram and stent placement are standard urologic procedures. Outcomes from the surgical procedure will be communicated to the patient or their designated family member per standard practice.*

### 9 STATISTICAL CONSIDERATIONS

#### 9.1 STATISTICAL HYPOTHESES

Primary Efficacy Endpoint: presence of reduced ureteral reflux in Relief stent compared to standard ureteral stent.

Comparative statistics will be employed between the two groups. Findings will be reported as the median and interquartile range (IQR) for continuous variables, and percentages and frequencies for categorical variables. To evaluate difference in the incidence of retrograde reflux (primary endpoint: present, absent) and grading between both arms (primary endpoint; Grades I, II, III, IV, V) Chi-square or Fishers exact test will be used as appropriate.

#### 9.2 SAMPLE SIZE DETERMINATION

At our target enrollment of 50 patients (25 patients in each arm), a power analysis for our primary endpoint (differences in incidence of retrograde urine reflux between randomized study arms) determined that our study will be sufficiently power (80%) to detect a moderate effect size ( $\omega = 0.4$ ) at an alpha level of 0.05.

#### 9.3 POPULATIONS FOR ANALYSES

To be eligible to participate in this study, an individual must meet all the following criteria:

1. Those who have capacity to consent
2. Stated willingness to comply with all study procedures and availability for the duration of the study
3. 18 years of age and up
4. Male or female subjects with confirmed ureteral and/or renal stones or strictures documented via abdomen X-ray KUB (kidney ureter bladder) or CT (computed tomography)

### 9.4 STATISTICAL ANALYSES

#### 9.4.1 GENERAL APPROACH

Findings will be reported as the median and interquartile range (IQR) for continuous variables, and percentages and frequencies for categorical variables. To evaluate differences in the incidence of retrograde reflux (Primary endpoint; present, absent) and grading between both arms (Primary endpoint; grades I, II, III, IV, V), chi-square or fishers exact test will be used as appropriate. To analyze USSQ findings between study arms (secondary endpoint), Mann-Whitney U test or independent t-tests will be used for comparisons of continuous variables and chi-square or fishers exact test for comparisons of categorical variables.

#### 9.4.2 ANALYSIS OF THE PRIMARY EFFICACY ENDPOINT(S)

To evaluate differences in the incidence of retrograde reflux (Primary endpoint; present, absent) and grading between both arms (Primary endpoint; grades I, II, III, IV, V), chi-square or fishers exact test will be used as appropriate.

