**Primary Objectives:**

- Assessment of retrograde urine reflux after placement of a ureteral stent using cystography after contrast gravity-filling of the bladder and assigning a urinary reflux grade based on the following standardized scoring system:
  - Grade I: urine refluxes into the ureter only.
  - Grade II: urine refluxes into the ureter and up to the kidney without dilation.
  - Grade III: urine refluxes into the ureter and kidney and causes mild dilation.
  - Grade IV: urine refluxes into ureter and kidney and causes dilation without twisting of the ureter.
  - Grade V: urine refluxes into ureter and kidney and causes significant dilation with twisting of the ureter.

- Evaluation of the stent placement and the adequacy of short-term drainage (defined as the presence of the stent in the ureter and the lack of surgical or other intervention to treat symptoms associated with the stent itself on the stented side during the first 48 hours).

[figure not shown]

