#### Day 0 (Stent Placement)

- Patients will be randomized to one of two study groups (Relief stent vs DJ stent)
- Medical charts will be reviewed and medications will be reviewed prior to surgery
- Stent will be placed per standard of care
- A intraoperative photo of the stent will be taken to confirm placement

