# 8 STUDY ASSESSMENTS AND PROCEDURES

## 8.1 EFFICACY ASSESSMENTS

The primary objective of the study is to assess whether the Relief stent causes reflux of urine. This will be assessed using a standardized grading system described previously. The additional objective of evaluating adequacy of short-term drainage uses the following definition: presence of stent in the ureter and lack of surgical or other intervention to treat symptoms associated with the stent itself during the first 48 hours. This will be determined during the phone interview or in person visit with the patient on

days 1 and 3 as well as by questionnaire. Medications used will be tracked on the research form per the timeline at days 1, 3, 7-10.

Screening will occur in the clinics to identify patients with stone disease who meet eligibility requirements and who require surgical treatment for their stones.

Patients who are deemed clinically suitable and choose to participate will be screened utilizing the EMR for recruitment. The urology provider will first determine if they are interested in participating in the research study and upon agreement, a study team member or research coordinator will introduce the study details and initiate a consent interview. If eligible, these patients will be approached during pre-surgical preoperative clinic visits by the research team to further explain the study and further address any of their questions and get their consent. Patients will be free to leave the study without any impact or influence on their clinical care or management at any point should they desire to do so.

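### Reflux grade is called a primary endpoint, but its listed levels leave out patients without reflux and its tests ignore the order of the grades

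*Combined protocol and SAP*

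**What the plan says.** Three sections of the combined protocol and SAP give grade the same label and the same tests. Section 9.4.2 plans to compare "grading between both arms (Primary endpoint; grades I, II, III, IV, V), chi-square or fishers exact test will be used as appropriate"; section 9.4.1 repeats this, and section 9.1 has "grading between both arms (primary endpoint; Grades I, II, III, IV, V) Chi-square or Fishers exact test will be used as appropriate". In each, the same sentence also names incidence, coded present or absent, as a primary endpoint.

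The scale is set out twice in section 3. It starts at "Grade I: urine refluxes into the ureter only" and rises in severity to Grade V. No level stands for no reflux. Section 8.1 adds only this: "This will be assessed using a standardized grading system described previously".

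Section 9.3, headed as the analysis populations, opens "To be eligible to participate in this study, an individual must meet all the following criteria" and repeats the inclusion criteria. It does not say who enters any analysis.

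The hypothesis in section 9.1 has a direction: "presence of reduced ureteral reflux in Relief stent compared to standard ureteral stent". The power statement in section 9.2 covers only "differences in incidence of retrograde urine reflux between randomized study arms". Mann-Whitney is named in sections 9.4.1 and 9.4.3, but only for USSQ scores.

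**The concern.** Two things are left open or chosen poorly for the grade comparison.

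**Who enters.** A patient without reflux has no grade on the listed scale. If the levels are taken as written, that patient drops out of the grade test. The test then compares refluxers in one arm with refluxers in the other. Whether a patient refluxes is itself what the stent is expected to change, so randomization no longer protects the comparison. A stent that removes the mildest reflux leaves behind a group that looks more severe.

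**Order.** Grades I to V are ordered and the hypothesis is a reduction. Chi-square and Fisher's exact test treat the levels as unordered names. The plan's latitude to use whichever is appropriate covers only these two tests. Ignoring order costs power when severity falls, and severity is what grade adds to present/absent.

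Two analysts could follow section 9.4.2 on the same data, one with refluxers only and one with all patients, and reach different conclusions on an endpoint labelled primary.

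**Working it through.** **1. The plan's own figure.** Inputs from section 9.2: N = 50 (25 per arm), w = 0.4, alpha 0.05. For a 2x2 table the noncentrality is N x w² = 50 x 0.16 = 8. With 1 df the power is 80.7%, so the stated 80% reproduces for present/absent. It does not carry over to grade. At the same w and N, an unordered test has 60.5% with 4 df (grades I-V, if all 50 patients had a grade) or 56.4% with 5 df (none plus I-V).

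**2. Assumptions.** The documents give no reflux rates and no grade distribution. Assumed for illustration:
- Split of control refluxers over I/II/III/IV/V: A = 20/40/25/10/5% or B = 40/35/15/7/3%.
- Reflux, control vs RELIEF: 70 vs 30%, 80 vs 40% or 90 vs 56% (w = 0.40, 0.41, 0.38).
- (a) Incidence and grade both fall by a proportional-odds shift. The odds ratio follows from the rates: (0.7/0.3)/(0.3/0.7) = 5.4; likewise 6.0 and 7.1.
- (b) Only incidence falls; same split in both arms.
- (c) Incidence falls little, severity clearly: 80% split A vs 65% split 60/30/8/2/0; 80% split B vs 65% split 70/25/5/0/0; 90% split A vs 75% split 55/30/10/5/0.
- (e) RELIEF only turns Grade I into none. Control 70, 80 or 90%; RELIEF 56, 64, 72% (A) or 42, 48, 54% (B).

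**3. How a refluxers-only test can point the wrong way.** Take case (e), split B, control 90%. As percentages of all control patients, the grades are 0.90 x (40, 35, 15, 7, 3) = 36.0, 31.5, 13.5, 6.3, 2.7. RELIEF moves the 36.0 to none and leaves the rest, so reflux is 54%. The mean rate is 0.72, and w = (0.90 - 0.54)/(2 x √(0.72 x 0.28)) = 0.36/0.898 = 0.40, the plan's own effect size. Among refluxers, Grade II or higher is 60% in control (35 + 15 + 7 + 3) and 100% in RELIEF. RELIEF looks worse, yet nobody has a higher grade.

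**4. Simulated power**, 25 per arm, two-sided 0.05, 20,000 trials per scenario. The refluxers-only figures for (c) come from a smaller run of 2,500 trials. FFH is the Fisher-Freeman-Halton test, that is, Fisher's exact test for more than two levels. It is the comparator because 97-100% of simulated six-level tables have over 20% of expected counts below 5. Present/absent power is by exact enumeration with chi-square.

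| Assumed pattern | Refluxers only, FFH | All patients 0-V, FFH | All patients 0-V, Mann-Whitney | Present/absent |
|---|---|---|---|---|
| (a) both fall | 6-36% | 68-83% | 87-96% | 82-87% |
| (b) only incidence falls | about 4-5% | 60-69% | 58-77% | 82-87% |
| (c) mainly severity falls | 27-56% | 36-61% | 58-80% | 23-30% |
| (e) only Grade I removed | against RELIEF: 17-26% (A), 57-76% (B) | 26-98% | 6-19% | 19-86% |

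In (a), on average 25 of 50 patients (25 x 0.70 + 25 x 0.30) to about 37 of 50 (25 x 0.90 + 25 x 0.56 = 36.5) would enter a refluxers-only test. Wrong-direction significance is about 1% or less in (a) and (c), and about 3% in (b), where the refluxers do not differ and any significant result is chance.

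**5. Type I error of each grade test alone.** With no difference between arms, six-level FFH rejects in 5.0-5.2% and Mann-Whitney in 4.7-5.1% of trials. Neither is inflated.

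**The case against.** **The inclusive reading is natural.** Absent stands beside the grades in one sentence, and the comparison is between both arms; absent plus I-V gives six levels. This stands in part. A reader might infer that the plan prescribes a refluxers-only analysis. It does not; it omits the wording that would exclude one. The inclusive reading is valid, and then only the point about order remains.

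**The wrong-direction result needs an extreme case.** Every Grade I patient must become reflux-free and nobody else may change. The rationale in section 2.1, closure of the ureteral orifice, does not suggest an effect confined to Grade I. This stands. Case (e) shows what can happen, not what to expect.

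**Refluxers-only power is not always low.** A reader might generalize from the 6-36% in (a). Case (c) gives 27-56%, above the 23-30% of the present/absent test there. This stands: power depends on the assumed pattern.

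**The rank test is not always better.** In (b) it runs from 4 points worse than FFH to 11 better, and in (e) it loses heavily. This stands, and is why present/absent should lead.

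**Incidence already leads.** Section 9.2 powers one endpoint, in the singular. A reader might infer two full primary tests with an inflated joint error; if both were read at 0.05, at least one false positive would occur in 6-10% of null trials with six-level FFH. But the power statement points to incidence, so an explicit label for grade settles this.

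**Conclusion.** The concern holds for the grade comparison. On the text alone, grade is labelled primary in three sections, its levels exclude patients without reflux, no analysis set is defined, and only unordered tests are named for an ordered scale. None of this depends on the simulations.

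The size does depend on assumed rates and splits. On the refluxers-only reading, the result can mislead in direction if the benefit is confined to Grade I, and power elsewhere ranges widely. On the inclusive reading, the test is valid but gives up 12-19 points of power in (a) and 13-22 in (c) compared with Mann-Whitney.

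A reader might infer that the trial's reflux comparison as a whole is invalid or underpowered. The documents do not support that: the present/absent comparison that section 9.2 powers is unaffected, and its 80% reproduces. This should be changed before outcome data are seen, but it does not threaten the trial.

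**What to change.** In sections 9.1, 9.4.1 and 9.4.2:
- Code no reflux as 0. Compare grade 0 to V by randomized arm, in all randomized patients with an evaluable post-stent cystogram, using the tie-corrected Wilcoxon-Mann-Whitney test.
- Report the probability of a lower grade, or a proportional-odds ratio, with a 95% confidence interval.
- Tabulate grade among refluxers descriptively only.
- Keep present/absent as the lead reflux analysis and label grade supportive, not a second route to claiming efficacy.
- State the downside: if only incidence or only Grade I changes, the rank test can have less power than the present/absent test, and for Grade I alone far less than the unordered test.

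A formal fixed sequence is not needed. If one is wanted, name a single present/absent test as the gate, since chi-square and Fisher differ in power (85.9% vs 78.2% at 70 vs 30%).

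The cost is wording in three sections and one added code for no reflux; no extra patients. Four related matters are separate points: scoring of missing cystograms, replacement of randomized patients under section 7.2, the cystogram missing from the schedule in section 1.3, and short-term drainage as the primary endpoint in the synopsis.
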